13.2.3 Data Analysis

Statistical analysis will be conducted by Chiesi, or its designee. Analysis of study data will be performed after the last subject has completed assessments for the Treatment Month 24 Visit or, in the case of subject undergoing HSCT or HSC-GT, the 6 -month follow-up visit.

Statistical analyses will be performed using Statistical Analysis Systems® (SAS®) Version 9.4 or later (SAS Institute, Cary, NC), or comparable software.

A complete description of data handling rules and planned statistical analyses is detailed in a separate Statistical Analysis Plan. Unless otherwise specified in this document or in the Statistical Analysis Plan, baseline is defined as the last measurement for a variable before the initial dose of Revcovi, and missing data will generally not be imputed. Baseline for the patients transitioning from the Phase III STP-2279-002 study is the last available non-missing value prior to the initiation of Revcovi in the STP-2279-002 study.

Analyses will be descriptive, with data listings, graphical presentations, frequency tabulations, and summary statistics as appropriate.

Each subject will serve as his/her own control based on the baseline assessment of each endpoint as appropriate, including changes in body weight as percentile on the growth curve, antibody formation, etc.

Exposure and safety summaries will be presented by whether or not they previously participated in study STP-2279-002.

Additional statistical analyses, other than those described in this section, may be performed if deemed appropriate to further explore the study data.

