6.5 Medical History

Medical history at screening will be listed, but not summarized.

6.6 **Prior ADA-SCID Treatment excluding ERT**

The number and percentages of patients who received prior ADA-SCID treatment (excluding ERT) will be summarized by type of treatment and overall. Free text for other treatments will be listed but not summarized.

6.7 **Prior ERT Treatments**

Prior ERT medications (Adagen treatment) will be summarized for all subjects transitioning from Adagen to Revcovi and for the STP 2279-002 subjects. The following parameters will be summarized: duration of Adagen treatment (i.e. last dose – first dose +1 day), units per administration, administration frequency, total weekly dose (as reported on the eCRF) and calculated total weekly dose per kg body weight for the prescribed and actual dose. For subjects who were treated according to the prescription, actual dose will be derived from the prescribed dose. The number and percentages of subjects who stopped Adagen treatment prior to the first dose will also be reported together with summary statistics for the time from the last dose of Adagen until the first dose of Revcovi. For the STP 2279-002 subjects, the duration of treatment with Revcovi in the STP 2279-002 study (last dose – first dose of Revcovi in the STP 2279-002 study + 1 day) will be summarized. All prior treatments with Adagen will also be presented in a data listing.

6.8 **Physical Examination**

Physical examination results at screening will be reported as medical history and will be analyzed and presented as such.

6.9 **Protocol Deviations**

A full list of protocol deviations will be presented in the clinical study report. Because this is a registry with no scheduled assessments or planned treatments, on-study protocol violations are restricted to administrative and operational deviations (e.g. delayed reporting of an SAE or transmission of clear names together with SAE reports). Protocol deviations will be listed but not summarized.

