For the STP-2270-002 subjects, the observational period for infections and hospitalizations after treatment initiation starts at the first dose of REVCOVI in the CLI-06814AA1-01 study. Infections and hospitalizations occurring during the STP-2279-002 study will not be included in the summary tables for the CLI-06814AA1-01 study.

The time periods will be defined as follows:

The year prior to treatment start with Revcovi will be defined as study day -365 to study day -1. For subjects younger than 1 year of age at the time of treatment initiation with Revcovi, it will be defined as the time period from the date of birth until study day -1 (time period calculated as date of first dose of Revcovi - date of birth + 1 day).

The end date of the time periods 1, 2, 3, 4, 5, 6, 7, 8, and 9 years after treatment initiation of Revcovi, respectively, will be defined as the earliest of the following events:

- End of time period (study day 365, 730, 1095, 1461, 1826, 2191, 2556, 2921, and 3286 respectively)
- Last date of treatment with Revcovi + 30 days
- Study completion date
- Study discontinuation date

- Date of death
- Date of transplantation

Infections occurring more than 30 days after the last dose of Revcovi will not be included in the calculation of the incidence rates, but will be included in the data listings and flagged.

The following analyses will be performed for the infections for each time period defined above:

- Number of events, number and percentages of affected subjects by SOC and PT. The denominator for the calculation of the percentages is the number of subjects with an observational period of 1 day or more in the respective analysis period, i.e. if the end date as defined above is not prior to the start date of the respective analysis period.
- Incidence rate of infections (in number of infections per year). The incidence rate will be based on the number of events, not on the number of affected subjects.
 95% CIs will be calculated for the incidence rates by the method of Ulm, assuming a Poisson distribution. The total observational period will be defined as the sum of the time periods for each subject from the start until the end date of the respective time period as defined above (end date start date + 1 day).

For both analyses, the infections will be slotted to the analysis periods based on the onset date of the adverse event.

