The number of hospitalizations will be analyzed similarly as the infections, i.e. number of hospitalizations, number and percentages of hospitalized subjects, incidence rates of hospitalizations for the time periods described above. The duration of hospitalizations will be described by descriptive statistics for continuous variables based on the number of hospitalizations. Subjects who are hospitalized in one analysis period and discharged from the hospital in the subsequent analysis period will be counted for the full hospitalization period (i.e. from admission to discharge) in the analysis period where they were hospitalized. All hospitalizations will also be presented in a data listing.

For subjects <18 years of age, height-for age and weight-for age and for patients between 24 months and 18 years of age, BMI-for age will be presented by z-scores at baseline and each intermediate collection time-point. Z-scores will be calculated programmatically based on reported age, gender, height and weight.¹ Z-scores and changes from baseline of z-scores to each visit (at which height and weight are assessed) will be summarized using descriptive statistics.

¹ http://www.cdc.gov/nccdphp/dnpao/growthcharts/resources/sas.htm

Overall survival will be analyzed by a Kaplan-Meier analysis. Kaplan-Meier survival curves will be plotted by subject status. Subjects who are alive at the end of the observational period will be counted as a censored observation. Observational period is the time from initiation of Revcovi until the date of study completion or study discontinuation (calculated as: date of study completion or study discontinuation – date of treatment initiation + 1 day) or from treatment initiation until the date of death, for subjects who die (calculated as date of death – date of treatment initiation + 1 day). Date of study completion or date of study discontinuation will be used as reported on the Patient Disposition page in the eCRF. For subjects transitioning from the STP-2279-002 study, overall survival will be calculated based on the date of the first dose of Revcovi in the STP-2279-002 study. If it is known that the subject died, but the date of death is unknown, it will be assumed that the subject died the day after their last assessment (whatever has been entered as last available date to the database, e.g. date of laboratory value, onset or resolution date of an AE, date of study discontinuation).

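### The pre-Revcovi period for infection and hospitalization rates ignores Adagen exposure and does not exclude the birth stay, so it is not a clean reference for rates on Revcovi

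*SAP*

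**What the plan says.** SAP 7.2.3 sets a series of periods for infections and hospitalizations, beginning with the year before Revcovi. "The year prior to treatment start with Revcovi will be defined as study day -365 to study day -1". For subjects under 1 year at first dose, "it will be defined as the time period from the date of birth until study day -1", with the length given as "time period calculated as date of first dose of Revcovi - date of birth + 1 day". Neither rule mentions Adagen.

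"The incidence rate will be based on the number of events, not on the number of affected subjects", over summed person-time, with Poisson confidence limits. "The number of hospitalizations will be analyzed similarly as the infections": the SAP lists "number of hospitalizations, number and percentages of hospitalized subjects, incidence rates of hospitalizations for the time periods described above". No text in either document excludes the birth admission or defines hospitalization so as to leave it out.

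The periods after treatment start are tied to exposure. They stop at the earliest of several events, among them 30 days after the last Revcovi dose and the date of transplantation.

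SAP 6.7 derives the duration of Adagen treatment from first and last dose and counts subjects who stopped Adagen before starting Revcovi, "together with summary statistics for the time from the last dose of Adagen until the first dose of Revcovi". Protocol 13.2.3.5 and SAP 8.2 both class infections and hospitalizations as efficacy measures. Protocol 13.2.3 states: "Each subject will serve as his/her own control based on the baseline assessment of each endpoint as appropriate".

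**The concern.** There is no control arm, and the pre-Revcovi rates are reported for the same periods, in the same form, as the rates on treatment. Readers will compare them.

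For Adagen-transitioning subjects the useful reference is time on Adagen. The window admits time before the first Adagen dose, which may contain the illness that led to diagnosis, and any gap between the two products. A fall after the switch could then reflect the earlier start of Adagen.

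For infants the window opens at birth. A recorded birth stay adds one event over a period that may be only weeks long, and it cannot recur after treatment starts. Part of any fall in the hospitalization rate would be built in.

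**Working it through.** **Inputs.** From SAP 7.2.3: the 365-day window, the infant length formula and event-based rates. The documents give no event rates, number of subjects with under a year of Adagen, number of newborns or age at first dose. Those are assumptions below.

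**Window lengths.** The plan states no rate to reproduce, but its period lengths can be checked. Day -365 to day -1 is 365 days, as labelled. Birth to day -1 inclusive is (first dose - birth) days, so the added day in the SAP formula makes it one too long: 31 instead of 30 days at a first dose 30 days after birth, or 3.3%. This slightly lowers infant rates.

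**Birth stay.** On the SAP's own length, one stay with first dose D days after birth gives a rate of 365.25/(D + 1):

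| D (days) | Hospitalizations per year from one birth stay |
|---|---|
| 30 | 365.25/31 = 11.8 |
| 60 | 365.25/61 = 6.0 |
| 90 | 365.25/91 = 4.0 |
| 120 | 365.25/121 = 3.0 |
| 180 | 365.25/181 = 2.0 |

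Take five such infants at D = 30, each with a birth stay and no other admission. Person-time is 5 × 31/365.25 = 0.424 years and the rate is 5/0.424 = 11.8 per year (95% CI 3.8 to 27.5, exact Poisson limits used here for the Ulm method). Without the birth stays it is 0, with an upper limit of 8.7.

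**Untreated time in the transitioning window.** Let u be the untreated share of the pooled pre-period and R the ratio of the untreated to the on-Adagen rate. The pre-period rate is then 1 + u(R - 1) times the on-Adagen rate. If Revcovi and Adagen rates are equal, the apparent fall is 1 - 1/(that factor).

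- One subject untreated for 6 of 12 months, u = 0.5: factor 1.5 (R = 2) to 2.0 (R = 3), an apparent fall of 33% to 50%.
- One subject untreated for 3 of 12 months, u = 0.25: factor 1.25 to 1.5, a fall of 20% to 33%.
- Pooled, 2 of 20 subjects untreated for 6 months, u = 2 × 0.5/20 = 0.05: factor 1.05 to 1.10, a fall of about 5% to 9%. At R = 5 the factor is 1.20.
- No such subject: factor 1.00.

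**Opposing effect.** If only a fraction c of pre-Revcovi events is captured, against full capture afterwards, the inflation cancels at c = 1/(1 + u(R - 1)). That is 1/1.05 = 95% to 1/1.10 = 91% in the pooled example, and 1/1.5 = 67% where the factor is 1.5.

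**Could affected subjects exist?** Protocol 9.2 calls for chronic ERT with Adagen but sets no minimum duration. Footnote 3 to Appendix 1, the transitioning schedule, restricts PedsQL at Treatment Week 12 and Month 9 to infants of 1 to 12 months. A child no older than 12 months at Month 9 began Revcovi at about 12 - 9 = 3 months or younger. The schedule thus provides for transitioning infants, whose window opens at birth, before any Adagen.

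**The case against.** All analyses are descriptive, and the SAP specifies no before/after contrast and never calls this period a comparator. The own-control sentence in Protocol 13.2.3 gives weight percentile and antibody formation as its examples, not event rates. This stands: the risk lies in how the tables are read, not in a test.

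The SAP is not blind to subject type. It truncates the window at birth and reports by subject status. Adagen-naïve subjects are therefore kept apart except in the overall column, and for them an untreated pre-period is appropriate apart from the birth stay. This stands too, but the split does not separate on-Adagen from untreated time within the transitioning group.

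That affected group may be small or empty. Protocol 7.1 and SAP 3.1 describe the Adagen patients as adults, although the synopsis and Protocol 9.2 do not. The 33% to 50% figures are for one subject, whereas the SAP pools. A birth stay matters only if sites enter it. Protocol 10.3 collects prior hospitalizations as part of disease history, and any birth stay that was entered would show in the listing.

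A reader might infer that these rules make Revcovi look better overall. The documents do not support that. Protocol 11.1 allows pre-Revcovi data to be gathered retrospectively where they exist. Infections are drawn from the adverse event dataset, while Protocol 12.1 assesses adverse events from the first registry dose. SAP 13.5 does define pre-treatment events, so capture is unknown, not nil. Under-capture and the extra infant day both lower the pre-Revcovi rate.

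**Conclusion.** The concern holds in limited form. The pre-Revcovi period is not a clean on-Adagen reference for transitioning subjects, and for infants it admits a birth stay that cannot recur. Each feature, taken alone, can raise the pre-Revcovi rate and exaggerate a fall.

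The size rests on assumptions. For transitioning subjects the pooled factor is 1.05 to 1.10 if 2 of 20 were untreated for 6 months at R = 2 to 3, and 1.00 if none were. For infant hospitalizations the effect is large wherever birth stays are recorded: 11.8 per year from one stay when the first dose is 30 days after birth.

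Net direction is not established, least of all for infections, where incomplete capture could cancel the inflation. The favourable direction is best supported for newborn hospitalizations. The change is worth making before the final analysis because it is cheap and removes an ambiguity from measures the plan itself treats as efficacy.

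**What to change.** In SAP 7.2.3:

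- **Adagen-transitioning subjects.** Split pre-Revcovi events and person-time into two reported lines. On-Adagen time runs from the later of day -365 and the first Adagen dose to the last Adagen dose plus the same 30-day allowance used for Revcovi, but no later than day -1. The rest is not-on-ERT time. Use the on-Adagen line as the reference for Revcovi rates. Flag subjects whose Adagen start date was imputed: SAP 14 sets a missing day and month to 1 July, which could misplace the cut by about six months.
- **Infants.** Do not count a routine birth admission as a hospitalization in the main pre-Revcovi rate. Keep it in the listing and show the rate with and without it. Keep every infant in the analysis, including those not discharged before the first dose, since dropping them could remove the sickest. Correct the extra day in the infant period length.

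The cost is SAP wording and programming. The SAP already uses Adagen dates, birth dates and hospitalization records. The downside is less on-Adagen reference person-time and a few more table lines.

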5. GENERAL ANALYSIS CONSIDERATIONS

All analysis will be descriptive and no statistical hypothesis will be tested. Descriptive statistics for continuous variables will include number of observations (n), mean, standard deviation (SD), median, minimum (min), and maximum (max); for categorial variables counts and percentages for each category. Ninety-five percent confidence intervals (CIs) will be calculated for the main outcome variables without adjustment for multiplicity to generalize the results to the general population. If not otherwise noted, confidence intervals for continuous variables will be based on normal distribution, for categorial variables on Clopper-Pearson (Clopper and Pearson 1934). Confidence intervals for Poisson distributions will be calculated by the method of Ulm (Ulm 1990).

Time to event analyses will be performed by the Kaplan-Meier method (Kaplan and Meier 1958). Confidence intervals for the median survival time will be calculated based on the method of Brookmeyer and Crowley (Brookmeyer and Crowley 1982) after log-log transformation.

All analyses will be performed by subject status (Adagen-Naïve subject, Adagen-Transitioning subject, or STP-2279-002 participant) and overall. Subject status is as collected on the Adagen/Revcovi Treatment page in the eCRF. There is a different recommended visit schema for the Adagen naïve subjects and the Adagen transitioning subjects (Table 1 and Table 2). However, a data review revealed that the timing of the assessments is not following the suggested visit schema. Therefore, the slotting schema within each subject status will be uniform for all assessments. All assessments will be slotted to the closest visit suggested for the Adagen transitioning or Adagen naïve subjects, respectively, regardless of whether or not the specific assessment is recommended for this visit, Participants of the STP 2279-002 study will be analyzed per the Suggested Schedule of Assessments for Adagen-Transitioning Subjects. Therefore, the visit windows will be specific for each type of subjects (see Section 13.3). All visits will be included in the overall column, regardless of whether or not the specific visit is analyzed for all type of subjects.

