7.2.3 Clinical status

Clinical status will be assessed through determination of the following:

- Infections will be determined and defined as either:
 - Clinically documented subjects with documented signs and symptoms of infection without positive microbiologic cultures
 - Microbiologically documented subjects with documented signs and symptoms of infection and with positive viral or bacterial cultures
- Hospitalizations incidence and duration of hospitalizations through completion of the study
- Growth height, weight and growth curve determinations through completion of the study (Note: this assessment should be done for subjects < 18 years of age)
- Overall survival through the end of the study

Infections will be extracted from the adverse event dataset as all reported adverse events where the question "Is this event an Infection?" is answered by "Yes" and the Classification is reported as "Clinically documented" or "Microbiologically documented". Events classified as "Unknown" will not be included in the analysis of the infections. However, events classified as Unknown will be included in the analysis of the adverse events as part of the safety analysis (see section 8.2). The following time periods will be analyzed:

1. The year prior to treatment start with Revcovi (study day -365 to -1)

- 2. From Treatment initiation until 1 year after treatment initiation with Revcovi (Study day 1 to 365)
- 3. From one to 2 years after treatment initiation with Revcovi (Study day 366 to 730).
- 4. From 2 to 3 years after treatment initiation with REVCOVI (Study days 731 to 1095)
- 5. From 3 to 4 years after treatment initiation with REVCOVI (Study days 1096 to 1461).
- 6. From 4 to 5 years after treatment initiation with REVCOVI (Study days 1462 to 1826).
- 7. From 5 to 6 years after treatment initiation with REVCOVI (Study days 1827 to 2191).
- 8. From 6 to 7 years after treatment initiation with REVCOVI (Study days 2192 to 2556).
- 9. From 7 to 8 years after treatment initiation with REVCOVI (Study days 2557 to 2921).
- 10. From 8 to 9 years after treatment initiation with REVCOVI (Study days 2922 to 3286).
- 11. At any time after treatment initiation with REVCOVI (Study day 1 onwards)

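### The Poisson (Ulm) intervals for infection and hospitalization rates leave out between-subject variability and are expected to be too narrow if subjects differ in their underlying rate

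*SAP*

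**What the plan says.** SAP 7.2.3 (Clinical status) defines the infection rate in three steps. The numerator is events: "The incidence rate will be based on the number of events, not on the number of affected subjects". The denominator is pooled person-time: "The total observational period will be defined as the sum of the time periods for each subject". The interval treats the pooled count as one Poisson variable: "95% CIs will be calculated for the incidence rates by the method of Ulm, assuming a Poisson distribution". SAP 5 repeats this as a general rule: "Confidence intervals for Poisson distributions will be calculated by the method of Ulm (Ulm 1990").

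The rate is reported for eleven periods: the year before Revcovi, nine successive treatment years, and a cumulative period from Study Day 1 onwards. SAP 5 adds the columns: "All analyses will be performed by subject status (Adagen-Naïve subject, Adagen-Transitioning subject, or STP-2279-002 participant) and overall".

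For admissions, SAP 7.2.3 says "The number of hospitalizations will be analyzed similarly as the infections" and goes on to list counts, percentages and incidence rates. It does not name an interval there.

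On purpose, SAP 5 says "Ninety-five percent confidence intervals (CIs) will be calculated for the main outcome variables without adjustment for multiplicity", and the same sentence gives generalization to the general population as the aim. SAP 7 adds that the intervals show the variability of the estimates.

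Neither document provides for overdispersion, a subject-clustered variance, a negative binomial model or a subject-level bootstrap, even as a sensitivity analysis.

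**The concern.** If the target is the rate in a wider population of patients, the enrolled subjects are a sample from it and the subject is the unit of variability. A Poisson interval on the pooled count carries only the chance variation of events given each subject's rate. It has no term for the spread of rates between subjects or for one infection leading to another in the same subject.

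The documents give reason to expect such a spread. Protocol 9.2 admits infants found by newborn screening, chronic Adagen patients, subjects bridging to transplant or gene therapy, and subjects who declined or did not respond to these. Protocol 5.1 describes phenotypes from severe early-onset disease to forms with residual enzyme activity. The overall column pools all three subject statuses.

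Infections and hospitalizations are called efficacy measures in Protocol 13.2.3.5 and SAP 8.2. With no hypothesis tests planned, the interval is the only formal statement of uncertainty on these rates. If it is too narrow, a period's rate, the cumulative rate, or a gap between naïve and transitioning subjects will look better determined than it is.

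**Working it through.** The plan gives no number of subjects, event rate, event count or dispersion, so it has no figure to reproduce. The check therefore uses the planned formula with assumed inputs.

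**Planned interval.** With d events in T person-years, in exact Poisson form:

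- lower limit = χ²(0.025; 2d) / (2T)
- upper limit = χ²(0.975; 2d + 2) / (2T)

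Example (assumed): 20 subjects, one year each, 20 events. The rate is 1.00 per year and the interval is 0.61 to 1.54.

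**What heterogeneity does.** Let subject i have rate λ_i, gamma-distributed with mean r and shape a, and follow-up t_i. Then Var(y_i) = r·t_i·(1 + r·t_i/a). With equal follow-up and m = r·t expected events per subject, the variance of the total is inflated by φ = 1 + m/a, and the true standard error is √φ times the Poisson one.

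- r = 1, t = 1, a = 1: φ = 2, √φ = 1.41
- r = 1, t = 1, a = 0.5: φ = 3, √φ = 1.73
- r = 1, t = 3, a = 1: φ = 4, √φ = 2.00

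Scaling the log-rate variance in the example gives exp(±1.96·√(φ/20)). That is 0.54 to 1.86 at φ = 2 and 0.47 to 2.14 at φ = 3, against 0.61 to 1.54 as planned.

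**Simulated coverage of the nominal 95% Ulm interval.** Assumed: n = 20, equal follow-up, 40,000 runs per cell.

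| Follow-up, rate per year | No heterogeneity | shape 2 | shape 1 | shape 0.5 |
|---|---|---|---|---|
| 1 year, 0.5 | 97.4% | 95.6% | 93.6% | 89.2% |
| 1 year, 1 | 95.7% | 90.2% | 84.7% | 76.2% |
| 1 year, 2 | 95.9% | 85.5% | 76.6% | 64.7% |
| 3 years, 1 | 96.1% | 81.3% | 70.3% | 56.6% |
| 3 years, 2 | 95.6% | 68.8% | 55.6% | 42.2% |

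For the cumulative period, with follow-up assumed uniform from 0.4 to 4 years and n = 20, coverage is about 59–82% at 1 per year and 44–71% at 2 per year over shapes 0.5 to 2. The shortfall grows with follow-up because φ grows with m.

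**Where it does not bite.** With no heterogeneity the interval is slightly conservative. In sparse one-year cells its conservatism can absorb mild heterogeneity: n = 10, 0.5 per year, shape 1 gives 94.5%.

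**Same subjects, two periods.** Two one-year periods were simulated in the same subjects, with stable rates, equal follow-up and no true change (n = 10 or 20, 1 or 2 events per year, shapes 0.5 to 2). The variance of the difference was about 0.98 to 1.02 times the Poisson value. A Poisson comparison rejected 3.5–4.7% of the time at nominal 5%. The subject effect largely cancels.

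**The alternative.** The envelope of the Ulm interval and a subject-clustered t interval on the log rate covered 92–95% in the n = 20 multi-year cells with shapes 0.5 to 2. At n = 6 to 10 it covered 90–97% in multi-year cells, against 46–92% for Ulm alone. Without heterogeneity it covered 97–99%.

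**The case against.** Several counter-arguments stand, at least in part.

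- **Recurrent counting is not the fault.** A reader might infer that Poisson fails because one subject can contribute several events. A sum of independent Poisson counts with different fixed rates is still Poisson; with 20 fixed unequal rates the Ulm interval covered 95.6–96.0% for that cohort's own rate. Undercoverage needs subjects viewed as draws from a wider population, or dependent events. The registry enrols every eligible patient, which makes a cohort-level reading plausible, but SAP 5 states the wider target.
- **Before/after comparisons.** A reader might also infer that the change from the pre-Revcovi year to the treatment years is made to look too certain. Largely the same subjects contribute to those periods, and stable rates cancel, as shown above. Treating clustered intervals for two such periods as independent would be too conservative: it rejected 0.0–1.5% in the same simulation. Dropout, or rates that drift within a subject, would weaken the cancellation.
- **Unknown size.** Every coverage figure rests on assumed dispersion, rates and numbers. The interval is expected to be too narrow; it has not been shown to be.
- **Hospitalizations.** The interval there is inferred from the instruction to analyze them similarly and from SAP 5. It is not stated.
- **Descriptive study.** There are no tests and no statistical stopping criteria. The number and percentage of affected subjects accompany each rate, and point estimates are unaffected. This lowers the priority, but it does not make the interval serve the purpose that SAP 5 gives it.

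**Conclusion.** The point holds in limited form, as a recommended change and not an essential one. As specified, the interval omits between-subject variability although it is meant to generalize beyond the cohort, so it is expected to be too narrow if subject rates differ or events within a subject are dependent.

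Under the assumed gamma heterogeneity with 20 subjects, actual coverage ranges from near nominal in sparse one-year cells to below 50% for the cumulative period at 2 events per year with strong heterogeneity. Which applies cannot be told from the documents.

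The consequence is overstated precision of single-period and cumulative rates and of comparisons between subject-status groups. The documents do not support two stronger readings: that before/after differences in the same subjects are generally overstated, or that a planned test has an inflated type I error, since none is planned. Hospitalization rates are affected to the extent that they take the same interval.

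**What to change.** Amend SAP 5 and 7.2.3 before database lock.

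1. Keep the event rate r = Σy_i / Σt_i as the estimate.
2. Compute the 95% interval on the log rate with the subject-clustered variance n/(n−1) × Σ(y_i − r·t_i)² / (Σy_i)² and a t quantile on n − 1 degrees of freedom.
3. Report the envelope with the Ulm interval: the lower of the two lower limits and the higher of the two upper limits. The envelope matters, because simply taking the wider interval does not guarantee coverage at least as good as each; the wider one need not contain the narrower.
4. Use Ulm alone when there are no events.
5. State that the same rule applies to hospitalization rates.

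The cost is a short SAP change and a few lines of code. The intervals will be wider, and slightly conservative where there is no heterogeneity. With very few subjects they become very wide: at n = 3, which late yearly periods could reach, a clustered-or-Ulm interval chosen by width was about 2 to 11 times the Ulm width at the median. Those cells should be read as showing little information about a wider population.
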